11.7.3. Proportional of Preterm Birth <37 weeks or \geq 37 weeks

If the delivery date is missing or unknown i.e. subjects withdrew from the study or lost to follow-up, the proportion of births data will be the missing data, which will be handled in below methods.

The analysis of proportion of preterm birth uses the *de facto* analysis. Missing data from subjects who withdraw from study participation will be imputed using last contact date or last record available in the study database. The last record are those clinical records that the subjects were last contacted but remained undelivered.

11.7.4. Length of Hospital Stay

The handling of missing data in neonatal hospital length of stay can be summarized as follows.

Length of hospital stay will be log-transformed (at base 10) and checked for normality prior to analysis. If the normality assumption holds, the missing values in the length of hospital stay will be multiple imputed and then analyzed using an analysis of covariance adjusting for the covariate of GA at entry and established progesterone use (yes or no). If the normality assumption is violated, the missing values will not be imputed and Wilcoxon rank sum test will be performed to compare the two treatments with all observed data.

If the length of stay data is log-normally distributed, the missing data (in log scale) will be imputed using the SAS® MI procedure with the regression method. The model includes treatment (TRT) and GA at birth (GA_birth) as predictors, where GA at birth is considered complete with missing values (if any) being imputed with the last contact date or last record available in the study database. The missing data will be filled in 1000 times to generate 1000 complete data sets. Sample SAS® code of the procedure can be found in below:

```
proc mi data=dsetin seed=xxx out=dsetmi n impute=1000;
  class TRT;
  monotone regression;
  var TRT GA_birth log_length_stay;
run;
```

Once the 1000 completed datasets are produced, analysis of the log-transformed length of hospital stay will be repeated on these imputed datasets, using a regression model to estimate the effect of treatment adjusting for GA at randomization (GA_rand) as continuous covariate and established progesterone use (EPU) as categorical covariate:

```
proc mixed DATA=dsetmi;
  class TRT EPU ;
  model log_length_stay = TRT GA_rand EPU / solution cl;
  lsmeans trtmt / cl diff;
  by _Imputation_;
```

```
ods output diffss=lgdiffs SolutionF=parameters CovB=covb;  
run;
```

PROC MIANALYZE will then be used to combine the results of analyses on the multiply imputed datasets based on Rubin's combination rules (Rubin, 1987):

```
proc mianalyze data=lgdiffs;  
  modeleffects estimate;  
  stderr stderr;  
  ods output PARAMETERESTIMATES=diffs_mi;  
run;
```

The combined results will be back transformed to normal scale afterwards.

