The Wilcoxon rank sum test will also be performed for length of hospital stay if the assumption of normality is violated after log transformation.

Additionally, interactions between GA at randomization and treatment and established progesterone use and treatment will also be investigated.

Other Secondary and Exploratory Analysis

Binary secondary analysis endpoints will be analyzed in a similar fashion to the neonatal composite analysis. Binary exploratory endpoints will be analyzed in a similar fashion to the key secondary endpoints. The details of analysis will be provided in the RAP.

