8.1.2. Planned Key Secondary Efficacy Statistical Analyses

Key Secondary Efficacy Statistical Analysis	
Endpoint	
	
 • Proportion of births prior to $37^{0/7}$ weeks' gestation • Proportion of births at term ($\geq 37^{0/7}$ weeks' gestation) • Length of neonatal hospital stay • Proportion of neonates with any diagnosis from the neonatal morbidity and mortality composite determined up to 28 days after EDD (of $40^{0/7}$ weeks) (details for each composite are provided in Section 11.5.4.)

To preserve the overall type I error rate, the key secondary analysis will be performed if and only if the null hypothesis of the primary endpoint is rejected. In addition, a sequential testing method will be used to adjust for multiplicity of the key secondary endpoints such that the type I error rate will be maintained at 5%. The sequential testing examines the hypothesis testing in a pre-specified order, i.e., the testing of the second secondary endpoint will be performed only if the first secondary endpoint is significant at 5%, and testing of the third secondary endpoint will be performed only if the first and second endpoints are significant at 5%.
 
Order of sequential testing is
 
 1) Length of neonatal hospital stay 2) Proportion of births prior to $37^{0/7}$ weeks' gestation and Proportion of births at term 3) Neonate composite outcome 	
Model Specification	

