	
 • For the endpoints of neonatal composite outcome, proportion of births prior to $37^{0/7}$ weeks' gestation, and proportion of births at term ($37^{0/7}$ to $41^{6/7}$ weeks' gestation), a logistic regression model will be used for comparing retosiban with atosiban, with GA at randomization and established progesterone use (yes or no) as covariates. The model will use a logit link function to estimate the log odds of percentage of preterm birth. The model will include terms for treatment group, established progesterone use, and GA at randomization. Additionally, interactions between GA at randomization and treatment and established progesterone use and treatment will also be investigated. • Length of hospital stay will be log-transformed (at base 10) prior to analysis. Log-transformed length of hospital stay will be analyzed using an analysis of covariance adjusting for the covariate of GA at randomization and established progesterone use (yes or no). Additionally, interactions between GA at randomization and treatment and established progesterone use and treatment will also be investigated. Wilcoxon rank sum test will also be performed to compare the two treatments if length of hospital stay is not log normal. • Terms fitted in the model will include: Fixed Categorical: TRT, EP and their interaction term (TRT*EP). Interaction will

Key Secondary Efficacy Statistical Analysis	
Fixed Continuous Covariates:	be included only if the interaction is statistically significant (at 0.1 level of significance). GA and interaction term (TRT*GA). Interaction will be included only if the interaction is statistically significant (at 0.1 level of significance).
Repeated:	None
SAS Code	

 Analysis of Covariance: <pre>ods output lsmeans=means diff=diffs tests3=tests; proc mixed data=xxx; class EP TRT; model log_LoS= TRT EP GA TRT*EP TRT*GA/ddfm=kr s; lsmeans TRT /pdiff cl alpha=0.05; run;</pre> Wilcoxon rand sum test: <pre>proc npar1way data=xxx Wilcoxon; class TRT; var log_LoS; ods output wilcoxontest=wtest; run;</pre> 	
Model Checking & Diagnostics	

 Refer to Appendix 9: Model Checking and Diagnostics for Statistical Analyses. 	
Model Results Presentation	

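### SAP 11.7.4 lets an undefined normality check choose the test, the covariate adjustment and the imputation for length of stay, and contradicts SAP 8.1.2 and the protocol

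*SAP*

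**What the plan says.** SAP 11.7.4 begins with a check on the outcome itself: "Length of hospital stay will be log-transformed (at base 10) and checked for normality prior to analysis". It then branches.

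- Pass: "If the normality assumption holds, the missing values in the length of hospital stay will be multiple imputed", followed by an ANCOVA adjusted for GA at entry and progesterone use. On the imputation: "The model includes treatment (TRT) and GA at birth (GA_birth) as predictors".
- Fail: "If the normality assumption is violated, the missing values will not be imputed and Wilcoxon rank sum test will be performed", using observed data only.

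Neither 11.7.4 nor Appendix 9 (SAP 11.9) names a normality test or a threshold.

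SAP 8.1.2 gives the rank test a different role: "Wilcoxon rank sum test will also be performed to compare the two treatments if length of hospital stay is not log normal". Protocol 8.3.5.1.2 agrees with 8.1.2: "The Wilcoxon rank sum test will also be performed for length of hospital stay if the assumption of normality is violated after log transformation". The code in 8.1.2 is "proc npar1way data=xxx Wilcoxon; class TRT; var log_LoS", with no covariates and no strata. The results paragraph of 8.1.2 commits, with no normality condition, to a model-adjusted stay per arm and a treatment difference with confidence interval and p-value.

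SAP 8.1.2 also places length of stay first in the list that follows "Order of sequential testing is". SAP 5.2 drops multiplicity adjustment because the study ended early.

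**The concern.** One look at the outcome settles three separate choices: which test is run, whether GA and progesterone use (the stratification factors) are adjusted for, and whether infants with missing stay are kept. Because the check is undefined, the analyst decides what counts as failure. The check is also aimed at the wrong quantity. An ANCOVA relies on the behaviour of its residuals and its treatment estimate, whereas 11.7.4 examines raw log stay before GA is taken into account.

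The sections then disagree on what a failure leads to. Under 11.7.4 the rank test replaces the ANCOVA, so adjustment and imputation are lost. Under 8.1.2 and the protocol it is added, so there are two p-values and no statement of which one counts. These are alternative harms, one for each reading. Even under the second reading, 11.7.4 withholds imputation once the check fails, so it is unclear whether the ANCOVA that is kept would be imputed.

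**Working it through.** The documents give no SD, effect, power or missing rate for length of stay, so there is no figure of theirs to reproduce. The size of the problem was assessed by simulation.

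**Inputs from the documents.** GA mix 7/13/27/53% and 55% early delivery on atosiban (Protocol 8.2.1); lower early-delivery shares (Protocol 8.2.2); 97 enrolled (SAP section 1); 300 with birth data as planned (Protocol 8.2.1); two-sided 5% level (Protocol 8.1).

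**Assumptions.** Term stay is about 3 days. Preterm stay is either until about 36 weeks plus 3 days (two-peaked) or log-linear in GA at birth (smooth). Log-SD is 0.4, or 0.5 term/0.7 preterm, or 0.8/0.9. The check is Shapiro-Wilk at 5% on raw log10 stay. The treatment effect, where there is one, is a 20-point fall in early delivery.

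**1. How often the check fails (55% early delivery, 500 runs each)**

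| Stay model | n | SD 0.4 | SD 0.5/0.7 | SD 0.8/0.9 |
|---|---|---|---|---|
| Two-peaked | 97 | 100% | 95% | 49% |
| Two-peaked | 300 | 100% | 100% | 96% |
| Smooth | 97 | 58% | 18% | 8% |
| Smooth | 300 | 99% | 59% | 26% |

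The definition of the check matters. Testing ANCOVA residuals instead gives 99%, 66% and 19% in the two-peaked case at n=97. Rounding stay to whole days gives 61% to 78% in the smooth case at n=97. With a truly lognormal stay, failure is about 5%.

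**2. No missing data.** Under the null, the two-stage rule (ANCOVA if the check passes, Wilcoxon if not) rejected in close to 5% of runs; the standard error at 500 runs is √(0.05 × 0.95/500) = 1.0 point. Power:

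| Stay model, SD | n | ANCOVA | Two-stage | Loss (points) |
|---|---|---|---|---|
| Two-peaked, 0.4 | 97 | 40.3% | 35.9% | 4.4 |
| Two-peaked, 0.5/0.7 | 97 | 35.9% | 33.9% | 2.0 |
| Smooth, 0.4 | 97 | 33.4% | 33.3% | 0.1 |
| Smooth, 0.5/0.7 | 97 | 28.3% | 27.3% | 1.0 |
| Two-peaked, 0.4 | 300 | 87.1% | 82.7% | 4.4 |
| Two-peaked, 0.5/0.7 | 300 | 80.7% | 77.9% | 2.8 |
| Smooth, 0.4 | 300 | 83.4% | 82.5% | 0.9 |
| Smooth, 0.5/0.7 | 300 | 68.3% | 67.7% | 0.6 |

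A separate simulation (2,000 trials per setting) assumed about 2.7 days at term, rising with weeks before 38, and odds ratios for early delivery of 0.5 and 0.35. ANCOVA against Wilcoxon was 38% vs 32% (6 points) and 66% vs 56% (10 points) at n=97, and 81% vs 73% (8 points) at n=300. Null rejection was 5% to 6% for both tests.

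**3. With missing stays** (two-peaked, SD 0.5/0.7, 1,000 runs, 20 imputations from treatment and GA at birth, GA at birth taken as known):

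| Setting | n | Imputed ANCOVA | Complete-case ANCOVA | Complete-case Wilcoxon |
|---|---|---|---|---|
| Null, about 10% lost, by arm and GA at birth | 97 | 6.5% | 11.6% | 12.1% |
| Same | 300 | 4.9% | 25.6% | 25.0% |
| Null, about 5% lost, by arm and GA at birth | 97 | 3.8% | 5.3% | 5.5% |
| Same | 300 | 5.5% | 10.1% | 8.7% |
| Null, about 9% lost, by GA at birth only | 97 | 4.9% | 4.5% | 4.6% |
| Same | 300 | 4.7% | 4.5% | 4.1% |
| Power, about 10% lost, by GA at birth only | 97 | 34.4% | 31.7% | 29.7% |
| Same | 300 | 79.0% | 77.3% | 73.4% |

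In the first two rows, 20% of stays were lost among preterm births in one arm and term births in the other, and none elsewhere; the 5% rows use 10% in place of 20%. Complete-case ANCOVA inflates as much as Wilcoxon, so the damage comes from dropping the imputation, not from using ranks.

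**The case against.** A prespecified rank-test fallback is common, and with complete data both tests hold their level. SAP 8.1.2, the main analysis section, keeps the ANCOVA and the adjusted estimate; 11.7.4 is a missing-data appendix. SAP 8.1.2 also plans a length-of-stay sensitivity analysis in the manner of SAP 7.1.2, which contains a covariate-adjusted mixture model and an ANCOVA. Missing data may be few: SAP 11.6.2.2 expects a missing delivery date to be unlikely. The type I inflation needs an asymmetric pattern of loss, and at n=97 with 5% loss it all but vanishes.

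Much of this stands, and it limits the size of the point. It does not settle which p-value is decisive, define the check, or say whether a retained ANCOVA is imputed. A sensitivity analysis cannot answer those questions.

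Two stronger readings are tempting and not supported. A reader might infer that the check is almost certain to fail. The two-component assumption in SAP 7.1.2 concerns time to delivery, not stay, and the failure rate at n=97 spans nearly the whole range. A reader might also infer that the first gate of a confirmatory sequence is at risk. SAP 8.1.2 sets out that sequence and opens it only after the primary null is rejected, but SAP 5.2 withdraws multiplicity adjustment, so whether any gate remains is unsettled.

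**Conclusion.** The point holds as a defect of specification and consistency. The rule in 11.7.4 is undefined, data-driven, and in conflict with 8.1.2 and the protocol over the analysis that counts. Failure of the check is likely if stays are clearly two-peaked, above all at n=300, but that shape is an assumption.

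With complete data the validity cost is negligible and the power cost modest. The serious consequence is conditional: it needs loss of about 10% tied to both arm and GA at birth. The protocol's 10% missing allowance concerns birth data; the documents give no rate or pattern for stay. The protection shown for the imputed ANCOVA also assumes that GA at birth is known. Where it is missing, 11.7.4 fills it from the last contact, and the protection would be weaker.

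**What to change.** In SAP 11.7.4, delete the normality switch. Name ANCOVA on log10 stay with treatment, GA at randomization and progesterone use, after the multiple imputation already described there, as the single test. Report the Wilcoxon test as a sensitivity analysis in all cases. Reword 8.1.2 to match, so that its adjusted difference and interval come from this model, and note the change from the protocol's conditional wording in SAP section 9. Reconcile 5.2 with the sequence in 8.1.2 by stating whether the order still governs inference.

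The cost is wording, to be settled before unblinding; the model and imputation code already stand in 11.7.4. The downside is reliance on approximate normality of the ANCOVA estimate with a non-normal outcome at n=97. ANCOVA stayed near its 5% level in the simulations with complete data, and the imputed version gave 3.8% to 6.5% under the null.

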11.8. Appendix 8: Values of Potential Clinical Importance

11.8.1. Laboratory Values for Pregnant Women

For laboratory parameters not listed below, the normal range defined in Quest will be used for analysis.

Haematology			
Laboratory Parameter	SI Units	Normal Range	
		Low Flag (< x)	High Flag (>x)
Eosinophils	Gl/L	0	0.6
Hematocrit	1	0.28	
Hemoglobin	G/L	95	
Lymphocytes, Abs	Gl/L	1.0	3.6
Lymphocytes	%	16	46
Total Neutrophil, Abs	Gl/L	3.9	13.1
Platelet Count	Gl/L	146	
Red Blood Cell Count (RBC)	Tl/L	12.7	15.3
White Blood Cell Count (WBC)	Gl/L	5.9	16.9

Clinical Chemistry			
Laboratory Parameter	SI Units	Normal Range	
		Low Flag (< x)	High Flag (>x)
Alanine transaminase (ALT)	U/L		25
Aspartate transaminase (AST)	U/L		32
Albumin	G/L	23	42
Bilirubin, total	UMOL/L		18.8
Chloride	MMOL/L	97	109
CO2 CONTENT	MMOL/L	20	32
Creatinine	UMOL/L		68.6
Glucose	MMOL/L	3.9	10
Magnesium	MMOL/L	0.45	0.90

Clinical Chemistry			
Laboratory Parameter	SI Units	Normal Range	
		Low Flag (< x)	High Flag (>x)
Phosphorus, INORG	MMOL/L	0.90	1.49
Potassium	MMOL/L	3.3	5.1
Sodium	MMOL/L	130	
Uric acid	UMOL/L		375

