14. Vital signs (blood pressure, pulse rate, respiratory rate, and temperature) will be assessed at Screening, as part of maternal safety monitoring during the Inpatient Randomized Treatment Phase and, if criteria are met, also during retreatment, and at the post-infusion assessment visit. During the Inpatient Randomized Treatment Phase and during retreatment, vital signs will be assessed and recorded within the following windows relative to the start of the infusion: 15 to 30 minutes, 4 to 8 hours, and 20 to 24 hours, at the end of the infusion, at the time of any dose changes, and as warranted by a medical condition. It is suggested (but not required) that oxygen saturation also be assessed at Screening and recorded in source documents.
15. Maternal subjects will complete the EPDS, a self-reported questionnaire, at the maternal follow-up assessment 6 weeks (-2 weeks/+6 weeks) after delivery.
16. The LFTs should be ordered from the local laboratory before dosing with the IP. If the local laboratory results are available before the start of dosing, confirm that ALT is not $\geq 2 \times$ ULN OR total bilirubin is not $> 1.5 \times$ ULN ($> 35\%$ direct bilirubin). An isolated bilirubin $> 1.5 \times$ ULN is acceptable if bilirubin is fractionated and direct bilirubin is $< 35\%$. Screening LFT laboratory results do not need to be available for the subject to be randomly assigned to treatment or for the start of dosing with IP; however, see Section 6.3.1 if ALT or bilirubin is abnormal.

17. Hematology, chemistry, and LFTs will be determined through a central laboratory at the screening, Day 2, and the face-to-face post-infusion assessment visits. The LFT values from the central laboratory should be reviewed for abnormalities (see Section 6.3.1). For subjects who deliver within 24 hours after completion or discontinuation of IP and for subjects who deliver at the investigative center after discharge but before the face-to-face post-infusion assessment visit, central laboratory assessments for hematology, chemistry, and LFTs should be performed. For subjects that do not deliver at the investigative center, central laboratory assessments for hematology, chemistry, and LFTs should be performed at the investigative center within 1 week (acceptable range: 3 to 14 days) after completion of the study drug infusion.
18. Prior to dosing, if the fetal heart rate pattern is nonreassuring, the subject cannot be dosed.

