6.3.12.5. Laboratory Assessments

The following laboratory tests will be performed locally:

- Liver function tests, including ALT and bilirubin, performed at Screening (see Section 6.3.1)

If additional nonprotocol-specified laboratory assessments are performed at the institution's local laboratory and result in a change in subject management or are considered clinically significant by the investigator (e.g., SAE or AE or dose modification), the results must be recorded on the subject's eCRF. Refer to the SPM for appropriate processing and handling of samples to avoid duplicate and/or additional blood draws.

With the exception of the above, all protocol-required laboratory assessments, as defined in [Table 5](#), must be performed by the central laboratory. For subjects that do not deliver at the investigative center, central laboratory assessments for hematology, chemistry, and liver function tests should be performed at the investigative center within 1 week (acceptable range: 3 to 14 days) after completion of the study drug infusion.

Laboratory assessments must be conducted in accordance with the Central Laboratory Manual and protocol Time and Events Table. Laboratory requisition forms must be completed and samples must be clearly labeled with the subject number, protocol number, site/center number, and visit date. Details for the preparation and shipment of samples will be provided by the central laboratory. Reference ranges for all safety parameters will be provided to the site by the central laboratory.

The biological samples collected over the course of the study that are directly related to the conduct and analysis of the study, including hematology and chemistry tests, and liver function tests are summarized further in [Appendix 5](#).

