8.2.5. Clinical Laboratory

Summaries for hematology and chemistry parameters will be performed using the Maternal Safety Population.

Summary tables presenting observed values and changes from baseline will be presented for clinical laboratory tests with numeric values by treatment group. Changes from baseline to each scheduled post-baseline visit will be presented.

The number and percentages of subjects with laboratory values outside the reference ranges will be summarized by treatment groups (hematology).

The subjects with laboratory values outside the reference ranges (hematology and chemistry) will be listed. The criteria for laboratory values outside of normal ranges are detailed in Appendix 11.8.1. If there are only the lower or upper ranges, only the lower or upper changes will be calculated for direction of interests.

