11.5. Appendix 5: Derived and Transformed Data

11.5.1. General

Multiple Measurements at One Time Point

- Mean of the measurements will be calculated and used in any derivation of summary statistics but if listed, all data will be presented.
- For laboratory assessment and vital signs' descriptive summary statistics and other endpoints, if there are multiple assessments within a same scheduled visit, the last assessment within the visit will be used.
- For laboratory assessment and vital signs with potential clinical importance, if there are two values within a time window, the worst value (i.e. the most extreme value from the normal range) will be used.
- Subjects having both High and Low values for Normal Ranges at any post-baseline visits for safety parameters will be counted in both the High and Low categories of "Any visit post-baseline" row of related summary tables. Unscheduled visit will be included. This will also be applicable to relevant Potential Clinical Importance summary tables.

Study Day

- Calculated as the number of days from the first study treatment date :
 - [1] Ref Date = Missing → Study Day = Missing (none displayed)
 - [2] Ref Date < First Study Treatment Date → Study Day = Ref Date – First Study Treatment Date
 - [3] Ref Date ≥ First Study Treatment Date → Study Day = Ref Date – (First Study Treatment Date) + 1

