11.11.5. Safety Tables

Safety Tables					
No.	Population	IDSL / TST ID / Example Shell	Title	Programming Notes	Deliverable [Priority]
Exposure					
3.01	Maternal Safety		Summary of Extent of Study Drug Exposure		
3.02	Maternal Safety		Summary of Inadequate Therapeutic Response		
Maternal Adverse Events					
3.11	Maternal Safety		Summary of Maternal Adverse Events		
3.31	Maternal Safety		Summary of Maternal Adverse Events by Maximum Grade or Intensity		
3.41	Maternal Safety		Summary of Most Common Maternal Adverse Events		
3.51	Maternal Safety		Summary of Maternal Serious Adverse Events		
3.71	Maternal Safety		Summary of Maternal Adverse Events of Special Interest		
3.72	Maternal Safety		Summary of Maternal Adverse Events of Special Interest by Gestational Age Group		

CONFIDENTIAL

GSK200721

Safety Tables					
No.	Population	IDSL / TST ID / Example Shell	Title	Programming Notes	Deliverable [Priority]
3.81	Maternal Safety		Summary of Maternal Disease-Related Adverse Events		
Fetal Adverse Events					
3.111	Maternal Safety		Summary of Fetal Adverse Events		
3.131	Maternal Safety		Summary of Fetal Adverse by Maximum Grade or Intensity		
3.141	Maternal Safety		Summary of Most Common Fetal Adverse Events		
3.151	Maternal Safety		Summary of Fetal Serious Adverse Events		
3.171	Maternal Safety		Summary of Fetal Adverse Events of Special Interest		
3.172	Maternal Safety		Summary of Fetal Adverse Events of Special Interest by Gestational Age Group		
Neonatal Adverse Events					
3.211	Neonatal Safety		Summary of Neonatal Adverse Events		
3.231	Neonatal Safety		Summary of Neonatal Adverse by Maximum Grade or Intensity		

CONFIDENTIAL

GSK200721

Safety Tables					
No.	Population	IDSL / TST ID / Example Shell	Title	Programming Notes	Deliverable [Priority]
3.241	Neonatal Safety		Summary of Most Common Neonatal Adverse Events		
3.251	Neonatal Safety		Summary of Neonatal Serious Adverse Events		
3.271	Neonatal Safety		Summary of Neonatal Adverse Events of Special Interest		
3.272	Neonatal Safety		Summary of Neonatal Adverse Events of Special Interest by Gestational Age Group		
3.281	Neonatal Safety		Summary of Neonatal Disease-Related Adverse Events		
Maternal Hospital Admission					
3.301	Maternal Safety		Summary of Maternal Hospital Admission (In-patient)		
Labs					
3.401	Maternal Safety		Summary of Observed Value and Change from Baseline in Hematology by Visit		
3.402	Maternal Safety		Summary of Hematology Results Outside the Reference Ranges by Visit		

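### The red cell count limits in SAP 11.8.1 (12.7 to 15.3 Tl/L) do not fit the same table's hematocrit and hemoglobin flags, and as written would flag essentially every reported RBC result low

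*SAP*

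**What the plan says.** The hematology table in SAP 11.8.1 (Laboratory Values for Pregnant Women) has one column for the low flag (below x) and one for the high flag (above x). The red cell row is "Red Blood Cell Count (RBC) Tl/L 12.7 15.3". The two related rows have low flags only: hematocrit 0.28 (as a fraction) and hemoglobin 95 g/L.

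SAP 8.2.5 makes this table operative: "The criteria for laboratory values outside of normal ranges are detailed in Appendix 11.8.1". The same section asks for numbers and percentages of subjects with out-of-range hematology values by treatment group, and for a listing. Both survive in the reduced set of displays in SAP Appendix 11: Table 3.402, "Summary of Hematology Results Outside the Reference Ranges by Visit", and Listing 113.

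Two other sources of ranges are mentioned. SAP 11.8.1 has a fallback: "For laboratory parameters not listed below, the normal range defined in Quest will be used for analysis". Protocol 6.3.12.5 says: "Reference ranges for all safety parameters will be provided to the site by the central laboratory".

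On timing of samples, Protocol Table 5, footnote 17 states: "Hematology, chemistry, and LFTs will be determined through a central laboratory at the screening, Day 2, and the face-to-face post-infusion assessment visits". The analytes in the hematology panel are not itemised anywhere.

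**The concern.** Red cell count, hematocrit and hemoglobin are linked through the volume and hemoglobin content of a cell, so limits for the three can be checked against one another. The RBC limits are several times higher than the other two rows allow. RBC has its own row, so the laboratory default for unlisted parameters does not replace it.

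A limit that nearly every result falls below does not separate normal from abnormal. The RBC line of Table 3.402 would report close to 100% low in both arms, and essentially every woman with an RBC result would enter Listing 113 on that basis. Truly low counts would be hidden among false flags, and a truly high count could not be identified.

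**Working it through.** **Inputs from SAP 11.8.1.** RBC low flag 12.7 and high flag 15.3 Tl/L (read as 10^12 cells per litre); hematocrit low flag 0.28; hemoglobin low flag 95 g/L.

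**Assumptions not in the documents.** Mean cell volume of 80 to 100 fL, shown over 50 to 110 fL; a generous upper hematocrit of 0.55; and, for a second route, 15 to 40 pg of hemoglobin per cell.

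**Formulas.** Hematocrit = RBC × cell volume (fL) / 1000. Hemoglobin (g/L) = RBC × hemoglobin per cell (pg).

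**Step 1: the three rows together.**
- Cell volume at the low flags: 0.28 / 12.7 × 1000 = 22.0 fL.
- Hemoglobin per cell at the low flags: 95 / 12.7 = 7.5 pg.
- Hemoglobin and hematocrit rows without RBC: 95 / 0.28 = 339 g/L of cells.

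**Step 2: a bound that needs no upper hematocrit.** Hematocrit cannot exceed 1.
- RBC of 12.7 requires a cell volume of at most 1000 / 12.7 = 78.7 fL.
- RBC of 15.3 requires at most 1000 / 15.3 = 65.4 fL.

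**Step 3: across assumed cell volumes.**

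| Cell volume (fL) | RBC at hematocrit 0.28 | 12.7 ÷ that RBC | Hematocrit needed for 12.7 | Hematocrit needed for 15.3 | RBC at hematocrit 0.55 |
|---|---|---|---|---|---|
| 50 | 5.60 | 2.27 | 0.635 | 0.765 | 11.0 |
| 80 | 3.50 | 3.63 | 1.016 | 1.224 | 6.88 |
| 90 | 3.11 | 4.08 | 1.143 | 1.377 | 6.11 |
| 100 | 2.80 | 4.54 | 1.270 | 1.530 | 5.50 |
| 110 | 2.55 | 4.99 | 1.397 | 1.683 | 5.00 |

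No entry in the last column reaches 12.7. At hematocrit 0.55 a result escapes the low flag only if the cell volume is 0.55 / 12.7 × 1000 = 43.3 fL or less.

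**Step 4: second route, through hemoglobin.** At 95 g/L, 15 pg per cell gives RBC 95 / 15 = 6.3, and 40 pg gives 95 / 40 = 2.4 Tl/L. Reaching 12.7 at 15 pg would need hemoglobin of 12.7 × 15 = 190.5 g/L; at 30 pg, 381 g/L.

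**Step 5: how much data.** The SAP synopsis reports 97 women enrolled and does not give the number dosed. With two scheduled post-baseline draws (Day 2 and the face-to-face visit), the ceiling is 97 × 2 = 194 scheduled results, or 97 × 3 = 291 if Screening is displayed. Retreatment, delivery-triggered and unscheduled draws would be extra.

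**The case against.** Four points can be made for the plan.

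- **Lower limits are marginal.** The three low flags need not occur in the same woman, so dividing one by another does not describe a real cell, and calling 339 g/L a sensible value relies on an outside norm. This is fair. Step 1 only shows where to look; the conclusion rests on Steps 2 to 4, whose assumptions are declared and varied widely.
- **The governing range is not entirely clear.** Appendix 8 is titled as values of potential clinical importance, Section 8.2.5 speaks of both normal and reference ranges, and the protocol has the central laboratory supplying ranges. The terms are mixed, but Section 8.2.5 points explicitly to 11.8.1, the fallback excludes listed parameters, and the protocol sentence concerns ranges sent to sites. Nothing lets another range override the row.
- **The effect is conditional and small.** It needs RBC to be reported and the row to be programmed as printed. Safety is descriptive, and a line near 100% in both arms would probably be noticed at first output. This stands and limits the weight of the point. An unrecorded repair by a programmer would nevertheless depart from the SAP, and SAP Section 9 rules out changes after unblinding.
- **Table 3.402 counts subjects, not results.** Correct. The 194 and 291 are ceilings on scheduled results, not the table's denominators.

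A shifted cell from PDF reading is unlikely: the RBC row has its own unit and both limits, and the neighbouring rows line up with their units.

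**Conclusion.** The RBC row is wrong as written. If it is programmed as printed and RBC is in the reported panel, about 100% of RBC results in both arms are flagged low for any mean cell volume of 50 to 110 fL at a hematocrit up to 0.55. At 80 to 100 fL the low limit is 3.6 to 4.5 times the count that corresponds to the table's own hematocrit flag. The high limit fails in the same way.

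The point is minor. It affects only the RBC flags in Table 3.402 and Listing 113. The postpartum hemorrhage assessment in SAP 8.2.3.6 uses change in hemoglobin, not RBC, and SAP 5.2 plans no formal test on safety data. The documents do not allow the intended range to be derived, nor show whether the value, the unit or the label is at fault.

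**What to change.** Before database freeze, trace the RBC row (label, unit and both limits) to its source and replace it with the verified range for pregnant women in Tl/L. If no such range can be found, delete the row so that RBC becomes an unlisted parameter under the SAP's laboratory default, and footnote Table 3.402 and Listing 113 that this default may not be pregnancy-specific. Confirm that the analysis dataset specification carries the corrected limits.

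The cost is one table row and one check of the specification; no new data are needed.
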